### 5.5. Study drug disposal and destruction

Study drug destruction at the investigational site will only be permitted if authorized by MethylGene/Mirati in a prior agreement and if permitted by local regulations.

# 6.1 CRITERIA FOR SUBJECT ELIGIBILITY

# 6.2 Subject Inclusion Criteria

Patients eligible for inclusion in this study have to meet **ALL** of the following criteria:

- Patient has provided a signed study Informed Consent Form prior to performance of any study related procedurePatient is ≥ 18 years of age
- Patient has histologically confirmed diagnosis of diffuse large B cell lymphoma or follicular lymphoma harboring mutations in CREBBP or EP300 with relapsed or refractory disease
- Patients with diffuse large B cell lymphoma must have received at least two prior therapies and have received, declined or be ineligible for autologous or allogeneic stem cell transplant.
- Patients with follicular lymphoma must have received at least two prior therapies.
- Patients with either diffuse large B cell lymphoma or follicular lymphoma will be allowed to enroll after receiving only 1 prior therapy if they are felt to not be a candidate for further systemic chemotherapy.
- Patient has at least one measurable lesion (≥ 2 cm) according to Cheson criteria [45]. Patient has an Eastern Cooperative Oncology Group (ECOG) performance status ≤ 1
- Patient has adequate bone marrow and organ function by:
  - Absolute neutrophil count (ANC)  $\ge$  1.0 x 10^9/L
  - Platelets  $\geq$  75 x 10^9/L (no platelet transfusion within past 14 days)
  - Hemoglobin (Hgb)  $\geq$  9.0 g/dL (no RBC transfusion within past 14 days)
  - International Normalized Ratio (INR) ≤ 1.5
  - Serum Creatinine  $\leq$  1.5 x upper limit of normal (ULN)
  - Alanine aminotransferase (ALT) and aspartate aminotransferase (AST) within 2.5 x ULN, or ≤ 5.0 x ULN for patients with documented hepatic involvement
  - Serum bilirubin ≤ 1.5 x ULN or ≤ 3.0 x ULN for patients with Gilbert Syndrome or documented hepatic involvement.
- Patients must have fully recovered from major surgery and from the acute toxic effects of prior chemotherapy and radiotherapy (residual grade 1 toxicity, e.g. grade 1 peripheral neuropathy, and residual alopecia are allowed)

# 6.3 Subject Exclusion Criteria

Patients eligible for this study must **NOT MEET ANY** of the following criteria:

- Patient has received previous treatment with HDAC inhibitors
- Patient has evidence of graft versus host disease (GVHD)
- Patient has active or history of central nervous system (CNS) disease
- Patient has impaired cardiac function including any of the following:
  - Presence or history of pericardial effusion (definitions are provided in Section 9.3.4) and/or pericarditis.
  - Acute myocardial infarction, symptomatic angina pectoris ≤ 6 months prior to starting study drug
  - Presence of congestive heart failure ≥ NYHA class 3

- QTc > 480 ms on a screening ECG
- Screening LVEF < 45% by echocardiography or MUGA

- Uncontrolled cardiac arrhythmia including uncontrolled atrial fibrillation/atrial flutter/sinus tachycardia, complete left bundle branch block, congenital long QT syndrome
- Presence of permanent cardiac pacemaker
- Other clinically significant heart disease
- Subject is taking warfarin at start of treatment or within 6 months prior to start of study treatment.
- Patient has a concurrent malignancy or has a malignancy within 3 years of study enrollment (with the exception of adequately treated basal or squamous cell carcinoma or non-melanomatous skin cancer)
- Patient is concurrently using other approved or investigational antineoplastic agent
- Patient has received chemotherapy, targeted anticancer therapy, pelvic and/or para-aortic radiotherapy or has had major surgery ≤ 4 weeks (6 weeks for nitrosourea, monoclonal antibodies or mitomycin-C) prior to starting study drug or who have not recovered from side effects of such therapy
- Patient has impairment of gastrointestinal (GI) function or GI disease that may significantly alter the absorption of mocetinostat (e.g., ulcerative diseases, uncontrolled nausea, vomiting, diarrhea, malabsorption syndrome, or small bowel resection)
- Patient is currently receiving increasing or chronic treatment (> 10 days) with corticosteroids or another immunosuppressive agent. The following uses of corticosteroids are permitted: single dose, topical applications (e.g., rash), inhaled sprays (e.g., obstructive airways diseases), eye drops or local injections (e.g., intra-articular).
- Patient has a history of non-compliance to medical regimen or inability to grant consent.
- Concomitant medications causing prolonged QT which cannot be discontinued or changed to a different medication prior to initiating study
- Patient is currently being treated with drugs known to be moderate or strong inhibitors or inducers of isoenzyme CYP3A, and the treatment cannot be discontinued or switched to a different medication prior to starting study drug. Patients must have discontinued strong inducers for at least one week and must have discontinued strong inhibitors before the start of treatment. Note: the oral anti-diabetic drugs troglitazone and pioglitazone are CYP3A inducers. Refer Appendix A, Table 20-1 to 20-5
- Patient has a known history of HIV (testing not mandatory), active Hepatitis B or C infection
- Pregnant or nursing (lactating) women, where pregnancy is defined as the state of a female after conception and until the termination of gestation, confirmed by a positive serum hCG laboratory test (> 5 mIU/mL)
- Women of child bearing potential and men with reproductive potential, if they are unwilling to use adequate contraception while on study therapy and for 3 months thereafter

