### 9.4.3. Prohibited concomitant therapy

**Other anticancer treatments:** Other anti-cancer treatment including chemotherapy and radiotherapy are prohibited during this study. If such agents are required, then the patient must be discontinued from the study.

**Growth factor support:** Prophylactic use of growth factor support to avoid anticipated study treatment side effects or as a substitute for a scheduled dose reduction. However they may be used in case of severe anemia (hemoglobin < 80 g/L or 8 g/dL) or neutropenia (< 1.0 x 109/L or 1000/ mm3) at discretion of the Investigator. Use of growth factors must be documented in CRDB.

**Warfarin or coumarin derivatives:** Therapeutic doses of warfarin or other coumadin derivatives anticoagulants are not permitted. Warfarin has a narrow therapeutic range and mocetinostat is possibly affected by CYP2C9, the main metabolizing enzyme of warfarin.

**Drugs with QTc prolonging activity**: As listed in Table 20.4. This list is not comprehensive and any questions should be reviewed with the pharmacist and discussed with the sponsor.

**CYP3A4 inhibitors and inducers:** As listed in Table 20.5. This list is not comprehensive and any questions should be reviewed with the pharmacist and discussed with the sponsor.

**Herbal medications/preparations**: Hernal medications and preparations are not allowed throughout the study, as a potential drug- drug interaction is always possible. These herbal medications include, but are not limited to: St. John's wort, Kava, ephedra (ma huang), gingko biloba, dehydroepiandrosterone (DHEA), yohimbe, saw palmetto, and ginseng. Patients should stop using these herbal medications at least 7 days prior to first dose of study treatment.

**Contraceptives:** Hormonal contraceptives may be affected by cytochrome P450 interactions, and are therefore not considered effective for this study, since induction of CYP3A4 may not be excluded in patients receiving mocetinostat.

**Gastric acid inducers:** Medications that directly increase gastric pH such as short-acting antacids should be avoided 4 hours before and 1 hour after administration of mocetinostat. Medications that affect gastric acid secretion, such as H2 antagonists or proton pump inhibitors will be allowed.

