#### 12.1. Measurability of lesion for objective response

- Measurable disease: lesions that can be accurately measured in two dimensions by CT, MRI, plain x-ray of other conventional technique and have a greatest transverse diameter of 2 cm or greater. Splenomegaly alone is not sufficient to qualify as measurable disease. PET scans alone are insufficient for evaluation of measurable disease.
- Non-measurable disease: All other lesions including unidimensional lesions, lesions too small to be considered measurable, pleural or pericardial effusions, ascites, bone disease, leptomeningeal disease, lymphangitis, pulmonitis, abdominal masses not confirmed by CT of disease documented only by indirect evidence (e.g. lab values).

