#### 12.2. Objective disease response assessment

Objective status is to be recorded at each evaluation according to the 2007 revised Cheson criteria [45]. All measurable lesions up to a maximum of 6 lesions (largest) should be identified as target lesions at baseline. If there are more than 6 measurable lesions, the remaining will be identified as non-target lesions and included as non-measurable disease. The 6 lesions should be selected according to the following features: they should be from disparate regions of the body and they should include mediastinal and retroperitoneal areas of disease if these sites have measurable lesions. Measurements must be provided for target lesions, while presence or absence must be noted for non-target measurable and non-measurable lesions.

- Complete response (CR): Complete disappearance of all measurable and non-measurable disease with the exception of the following. In patients with positive PET prior to therapy, a post treatment residual mass of any size is permitted as long as it is PET negative. If the PET scan was negative prior to therapy, all nodal masses > 2 cm in greatest transverse diameter (GTD) at baseline must have regressed to ≤ 2 cm in GTD and all nodal masses > 1 cm and ≤ 2 cm in GTD and > 1 cm in their short axis before treatment must have regressed to ≤ 1 cm in their short axis. No new lymphoma lesions should be visible on PET scan or by any other imaging studies. The spleen and/or liver, if considered enlarged at baseline based on physical examination or imaging study (other than PET), must have regressed in size and must not be palpable. If bone marrow was positive at baseline, it must be negative based on biopsy and aspirate at the same site. Normalization of markers (i.e. LDH) definitely assignable to DLBCL or FL. Tumor measurements must be obtained by an imaging modality other than PET. All disease must be assessed using the same technique as baseline unless clinically contraindicated.

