#### 12.3. Best objective response

- CR: one objective status of CR documented before relapse
- PR: one objective status of PR documented before progression but not qualifying as a CR

- Stable: at least one objective status of stable disease documented at least 6 weeks after registration, no qualifying as a CR or PR
- Increasing disease: objective status of progression within 12 weeks of registration not qualifying as CR, PR or SD
- Inadequate assessment, response unknown: progression greater than 12 weeks after registration and no other response category applies

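### The timed radiotherapy exclusion covers only pelvic and para-aortic fields and no rule handles irradiated lesions, so shrinkage from recent radiotherapy elsewhere can be scored as a mocetinostat response.

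*Combined protocol and SAP*

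**What the plan says.** **Eligibility.** The only timed radiotherapy criterion is in Section 6.3. It names two fields and a window: "Patient has received chemotherapy, targeted anticancer therapy, pelvic and/or para-aortic radiotherapy or has had major surgery" within 4 weeks before starting study drug, or failure to recover from the side effects of such therapy. Section 6.2 adds a condition on toxicity, without an interval: "Patients must have fully recovered from major surgery and from the acute toxic effects of prior chemotherapy and radiotherapy", with residual grade 1 toxicity allowed. Section 6.3 also excludes concurrent treatment: "Patient is concurrently using other approved or investigational antineoplastic agent". That concerns agents in current use, not a completed course of radiotherapy. One measurable lesion of at least 2 cm is enough for entry (Section 6.2).

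**On study.** Section 9.4.3 covers every field: "Other anti-cancer treatment including chemotherapy and radiotherapy are prohibited during this study". A patient who needs such treatment must come off study. The text does not say whether the study begins at consent, registration or first dose.

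**Response.** The measurability section (the second one numbered 12.1) goes by technique and size: lesions must be measurable in two dimensions and "have a greatest transverse diameter of 2 cm or greater". Section 12.2 takes up to six of the largest lesions, from disparate regions, and adds that "they should include mediastinal and retroperitoneal areas of disease if these sites have measurable lesions". Partial response needs a fall of at least 50% in SPD with no new lesions. Section 12.3 asks for no confirmation: "PR: one objective status of PR documented before progression but not qualifying as a CR". None of these sections mentions previously irradiated lesions.

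**Baseline scan.** Section 8.1 and Table 10-1 allow it up to 28 days before treatment. Section 10.2.2 allows 21 days and prefers 7. None requires it to follow the last radiotherapy.

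**The concern.** This is a single-arm trial whose primary endpoint is tumour shrinkage, with no control group to show what recent radiotherapy would have done alone. The plan treats radiotherapy to any site as unacceptable during the study, yet treats only two fields that way just before it. Section 12.2 also asks for measurable mediastinal disease to be among the targets, and the mediastinum lies outside the timed exclusion.

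A patient whose main mass is in the neck or mediastinum could be irradiated shortly before day 1, recover from acute toxicity, enter with that mass as a target lesion, and be scored as a partial responder at the week 8 scan. If the baseline scan came before the radiotherapy, shrinkage that occurred before the first dose would count as well.

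Each cohort is declared a success on 7 responses in 25, so one or two misattributed responses per cohort matter. An early one can also carry an inactive regimen past the futility rule and lead to 15 more patients being treated.

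**Working it through.** **Step 1: is the route open?** Each rule that might close it, side by side:

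| Rule | Reaches radiotherapy outside the pelvic and para-aortic fields, completed before entry? |
|---|---|
| 6.3 timed exclusion | No; names two fields only |
| 6.2 recovery criterion | Only while acute toxicity exceeds grade 1 |
| 6.3 concurrent agents | No; current use only |
| 9.4.3 prohibition | No; applies during the study |
| 12.1 and 12.2 measurable and target lesions | No mention of irradiated lesions |
| 12.3 best response | No confirmation needed |

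The route is open in the text.

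**Step 2: reproduce the plan's error rate.** Inputs from Section 14.0: null rate 0.15, target rate 0.40; stage 1 has 10 patients and continues with 2 or more responses; the drug is effective with 7 or more of 25. With X1 ~ Bin(10, p) and X2 ~ Bin(15, p):

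P(effective) = Σ over x = 2 to 10 of P(X1 = x) × P(X2 ≥ 7 − x).

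At p = 0.15:
- x = 2: 0.2759 × 0.0617 = 0.0170
- x = 3: 0.1298 × 0.1773 = 0.0230
- x = 4: 0.0401 × 0.3958 = 0.0159
- x = 5: 0.0085 × 0.6814 = 0.0058
- x = 6: 0.0012 × 0.9126 = 0.0011
- x ≥ 7: 0.0001

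The sum is 0.063, which is the stated 6%. The early-stop probability is 0.85^10 + 10 × 0.15 × 0.85^9 = 0.197 + 0.347 = 0.544, as stated. At p = 0.40, P(effective) = 0.900, which agrees with the stated type II error of about 10%.

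**Step 3: misclassify a share of non-responders.** Let f be the share of drug non-responders who are scored as responders because of radiotherapy. The apparent rate is p = 0.15 + 0.85f, and the expected number misclassified in 25 patients is 25 × 0.85 × f.

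| f (assumed) | Apparent rate | Expected misclassified of 25 | P(effective) |
|---|---|---|---|
| 0 | 0.150 | 0 | 0.063 |
| 1% | 0.1585 | 0.21 | 0.080 |
| 2% | 0.167 | 0.43 | 0.100 |
| 4% | 0.184 | 0.85 | 0.148 |

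Here f counts patients actually misclassified. If instead 4% of all patients are recently irradiated and such a patient is scored a responder with probability 0.5 to 1, the apparent rate is 0.15 × 0.96 + 0.04 × (0.5 to 1) = 0.164 to 0.184, and P(effective) is 0.093 to 0.148.

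**Step 4: exactly one false responder per cohort.** Fix one patient as a responder and keep the other 24 at 0.15. If that patient is in stage 2, P(effective) = 0.121; if in stage 1, 0.136. In the stage 1 case the early-stop probability falls from 0.544 to 0.85^9 = 0.232, because one response among the other nine is then enough to continue.

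**The case against.** The other side has several good points.

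- **Recovery is required.** Section 6.2 demands recovery from acute radiotherapy toxicity, and the 6.3 criterion repeats a recovery condition for the therapies it lists. This narrows the case of radiotherapy just before day 1. It is not an interval and does not close the case.
- **One irradiated mass need not make a response.** The SPD covers up to six lesions from disparate regions, new lesions rule out a partial response, and splenic and hepatic lesions must also regress by half. A reader might infer that radiotherapy shrinkage simply counts as a drug response. The documents support only that it can, when irradiated disease dominates the SPD. Where the only measurable lesion was irradiated, there is no dilution.
- **The error is not strictly one-way.** A reader might infer that it can only add responders. It could also remove one: an inert residual mass kept as a target can dilute true shrinkage, and progression is measured from the smallest sum, so regrowth after radiotherapy can count against the drug. Upward bias is the likely direction; the documents do not show it to be the only one.
- **The study may begin at consent.** Section 8.1 places the remaining screening assessments after main consent. If the 9.4.3 prohibition starts there, radiotherapy between a screening scan and day 1 is barred. The start is undefined, and radiotherapy before consent but within 4 weeks of day 1 stays open on either reading.
- **The cited response criteria may deal with irradiated lesions.** Section 12 relies on published criteria that are not reproduced in the plan. The finding is about the protocol's own text.
- **The size is assumed.** No rate of recent radiotherapy is given, and the number affected could be zero. It would also be loose to equate f = 4% with one patient in 25: it corresponds to 0.85 expected misclassifications.

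These points limit the wording and the size. None closes the gap.

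**Conclusion.** The concern holds in a limited form. As written, the plan can admit a patient recently irradiated outside the pelvic and para-aortic fields, and it can credit the resulting shrinkage to the drug on a single assessment. This needs acute toxicity recovered to grade 1 or less and irradiated disease that dominates the SPD. The likely effect is to raise the false-positive rate: from 0.063 to between 0.080 and 0.148 if 1% to 4% of drug non-responders are misclassified, and to between 0.121 and 0.136, about double, with exactly one false responder in a cohort. These figures take the true drug rate as 15%. The misclassified share is an illustration and not an estimate, because the documents give no figure for it. The gap in the text is certain; its practical impact is not known.

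The 28-day and 21-day baseline scan windows also conflict. That is a separate inconsistency, which neither creates nor cures the radiotherapy gap.

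**What to change.** 1. In Sections 12.1 and 12.2, state that a previously irradiated lesion may not be a target lesion, or the sole qualifying measurable lesion, unless it has grown on imaging since that radiotherapy.
2. In the same place, state that the baseline scan must follow the last radiotherapy.
3. Reconcile the radiotherapy scope of the 6.3 criterion (two fields) with 9.4.3 (all radiotherapy), and say when the 9.4.3 prohibition begins. Whether an interval should apply to other fields, and how long it should be, is a clinical decision for the sponsor and investigator; none is proposed here.
4. Separately, state one baseline scan window in Section 8.1, Section 10.2.2 and Table 10-1.

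These are wording changes. The sample size, decision rule and analysis stay as they are. The cost is that a few patients will need another measurable lesion or a repeat baseline scan.

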### 7.0 RECRUITMENT PLAN

Patients will be recruited by the treating team of physicians and medical professionals. Patients will be treated by the lymphoma service at MSKCC. Given the diverse population of patients at MSKCC, we expect that minorities and women patients will have full access to this study and will be

fairly represented in the accrual. The study procedures and requirements will be clearly presented in the molecular prescreening consent form and the consent form and explained to all patients at the time the consent is obtained. The principle investigator, [name], MD, PhD, will be available to all patients for further questions and information through a contact number provided on the molecular prescreening consent and the therapeutic consent.

### 7.1 Molecular pre-screening

Only patients with mutations in CREBBP or EP300 will be eligible for enrollment into this study. For patients with documented mutation of CREBBP or EP300, molecular pre-screening will not be needed. For patients with unknown CREBBP or EP300 status, tumor biopsies will be tested. Tumor mutational testing will be performed in the MSK Department of pathology Diagnositc Molecular lab using protocol 12-245. Mutational testing performed via the MSK-DMP on the IMPACT panel will require normal tissue/blood for germline comparision to identify mutations.

Only patients that exhibit a CREBBP/EP300 mutation as described below (in addition to all other inclusion/exclusion criteria) will be eligible for subsequent study enrollment. We anticipate pre-screening approximately 100 patients in order to enroll 27 in each cohort.

CREBBP and EP300 mutation is confirmed if:

Direct sequencing results confirm the presence of a CREBBP or EP300 mutation (deletion, frameshift, nonsense, missense) affecting CREBBP or EP300 as previously described [1] or via corroboration with the COSMIC database.

### OR

Should mutations be identified that have not been previously described, patients may be enrolled following discussion and agreement of the principle investigator on consultation with MethylGene/Mirati. The method used and the result should be entered into CRDB.

### 8.0 PRETREATMENT EVALUATION

### 8.1. Screening

After signing the main study informed consent form for the study, the remaining screening assessments will be done generally within 7 to 28 days prior to start of treatment (Table 8-1). Please note that the screening period must not exceed 28 days.

- Medical history and demographics
- Complete history and physical exam (including weight, pulse, blood pressure, temperature, ECOG performance status)
- Medication review
  - Bloodwork 14 days prior to starting therapy:
    - CBC with differential
    - Comprehensive metabolic panel, LDH, magnesium, phosphorus
    - Liver function tests
    - Uric acid

- Coagulation tests with PT/PTT and INR
- HIV testing
- Hepatitis B and C testing
- ECG
- Pregnancy test will be performed for women of child bearing potential
- Echocardiogram at baseline
- Evidence of disease evaluation within 28 days prior to starting treatment
  - CT scan with contrast, unless contraindicated, of the chest, abdomen, and pelvis
  - CT scan with contrast, unless contraindicated, of the neck as clinically indicated
  - PET scan for patients with DLBCL
  - MRI may be substituted for CT scan if patients are intolerant of CT scans with contrast
  - Archival or fresh tumor biopsy for confirmation of CREBBP and/or EP300 mutation

